7.7. Discontinuation/Withdrawal of Participants from Study

Each participant has the right to withdraw from the study at any time. In addition, the Investigator may discontinue a participant from the study at any time if the Investigator considers it necessary for any reason including:

- Pregnancy
- Ineligibility (either arising during the study or retrospectively having been overlooked at screening)
- Significant protocol deviation
- Significant non-compliance with treatment regimen or study requirements
- Withdrawal of Consent
- Loss to follow up

After the initial participant visit for the participant experience questionnaire and collection of data from participant notes no further observations will be required.

Withdrawal of consent from a participant will exclude the data for that participant from analysis.

Withdrawn participants will NOT be replaced.

The reason for withdrawal will be recorded in the CRF.

7.8. Definition of End of Study

The end of study is the date of the last visit / telephone follow up / home visit of the last participant which is expected to be on or around 30th November 2019.

8. INTERVENTIONS

The flow chart for all participants in the Spinal Motion Restriction Feasibility Study is shown in appendix D.

Intervention group: Over a six-month period intervention group patients (suspected cervical spine injury – see appendix A for guidelines) will be transported by NEAS crews to the randomised intervention site. See appendix B for SMRF Study Intervention Group Guideline.

Participants will have their cervical spine motion restriction managed in accordance with the proposed flow chart (see appendix B). For these patients unless the exclusion criteria apply, NO rigid collars will be used. The control group will follow existing clinical guidelines and use a rigid collar (appendix E).

9. SAFETY REPORTING (Adverse Event Management)

Use of hard collars in association with blocks and tapes in the manner described above has been accepted practice to reduce the risk of further damage due to movement of potentially unstable injuries for many years. Although there appears to be mounting expert opinion that the application of hard collars may cause more harm than good we must be vigilant against the potential of causing more harm in these patients. If there should be a case of new neurology developing post transfer during the study period the trial would need to be halted while a full and thorough investigation was undergone into whether the use of or lack of a hard collar caused or contributed to deterioration in neurological function. This study is not aimed at underplaying the risk of SCI or the need for appropriate management.

9.1. Definition of Serious Adverse Events

An adverse event is 'Any untoward medical occurrence in a patient or clinical investigation participant taking part in health care research, which does not necessarily have a causal relationship with the research.

A serious adverse event is any untoward medical occurrence that:

- results in death
- is life-threatening
- requires inpatient hospitalisation or prolongation of existing hospitalisation
- results in persistent or significant disability/incapacity
- consists of a congenital anomaly or birth defect.

Other 'important medical events' may also be considered serious if they jeopardise the participant or require an intervention to prevent one of the above consequences.

NOTE: The term "life-threatening" in the definition of "serious" refers to an event in which the participant was at risk of death at the time of the event; it does not refer to an event which hypothetically might have caused death if it were more severe.

9.2. Reporting Procedures for Serious Adverse Events

A serious adverse event (SAE) occurring to a participant should be reported to the REC that gave a favourable opinion of the study where in the opinion of the Chief Investigator the event was 'related' (resulted from administration of any of the research procedures) and 'unexpected' in relation to those procedures. Reports of related and unexpected SAEs should be submitted within 15 working days of the Chief Investigator becoming aware of the event, using the HRA report of serious adverse event form (see HRA website).

All of the patients in this study will have experienced an acute injury requiring an emergency ambulance for transportation to either a trauma unit or major trauma centre and as such will be expected to have

CONFIDENTIAL: Spinal Motion Restriction Feasibility Study (SMRFS).

injuries from the initial insult of the trauma. Through monitoring of the receiving sites, it is believed that if there is an obvious deterioration/change between pre and post management of the intervention group compared to the control group then the incident must be reported and study halted.

All serious adverse events should be reported to the site primary investigator and chief investigator using the appropriate form at the earliest opportunity. (See appendix F)

9.3. End of the Study

The study will end when the final patient has been recruited and their outcomes extrapolated from the patient notes or classified as lost to follow up. This is believed to be approximately 7 months from the start of participant recruitment.

The study will be stopped prematurely if:

- Mandated by the ethics committee,
- There is an obvious differentiation between the outcomes of control and intervention groups,
- There is a serious adverse event which prevents the ongoing study to be viable.

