Based upon the limited literature the aim of this study is to determine if there is a difference in clinical outcomes and patient experience, as well as the experiences of the clinicians taking part in the study, comparing traditional immobilisation techniques, which include a rigid collar versus Spinal Motion Restriction (SMR) techniques which include the omission of a rigid cervical spine collar.

Brief description of the intervention:

Patients experiencing a mechanism of injury that would suggest a potential spinal injury will have the JRCALC immobilisation guidelines (Canadian C spine rules) applied on assessment. If, after assessment, the patient is positive for spinal stabilisation then the intervention group will apply Spinal Motion

Restriction (SMR) principles which omit the use of a rigid collar. The patient will be manged as standard with the only change being the omission of the rigid collar. To assist is providing a visual marker for the patients ongoing management an additional sticker will be placed upon the head blocks/tape/blanket rolls which states 'C-Spine NOT Cleared'. Participants from both the control and intervention groups as well as the clinicians themselves will be asked to complete an experience questionnaire after the event.

Risks and benefits: There is little evidence for or against rigid collar use. There is a potential that if patients are managed poorly (rough handling) then neurology may be compromised. The benefits are that on scene times may be reduced (patient comfort through environmental factors) and overall patient comfort will be improved and reducing the risk of pressure sores and associated risk of infection.

The study is applicable to any patient experiencing a significant mechanism of injury that would suggest a spinal cord injury such as (but exclusive to) fall from height, Road Traffic Collision, assaults etc. It is believed the results of the study will be generalised and applicable to the wider trauma population with potential spinal cord injury. It in no way underplays the seriousness or risks associated with a spinal cord injury.

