5. STUDY DESIGN

Participants will be pre-randomised based on the hospital sites they are attending. Northumbria Specialist Emergency Care Hospital (NSECH) and James Cook University Hospital (JCUH) are the two nominated research sites. Initially the two participating sites will be randomised to either intervention or control site. After six months duration the sites will reverse and whichever site was originally randomised as intervention site will become the control site for the remaining six months and the control site will become the intervention site.

The participants will be selected by the attending trained North East Ambulance Service (NEAS) personnel and enrolled into the study if they are positive for a mechanism of injury and clinical assessment that would suggest a Spinal Cord Injury. NEAS are acting as the Participant Identification Centre (PIC) for patient participants and research site for clinical experience.

Control group: Over a six-month period this group will be managed in the traditional manner. This will involve patients being advised of the need for a hard collar, blocks and tape. For a variety of reasons this may not be tolerated by some patients and this non-compliance will be recorded for the purposes of the study outcome results, although these patients will be included in the 'traditional' method of motion restriction numbers.

Intervention group: Over a six-month period intervention group patients transported by NEAS crews with a suspected cervical spine injury being taken to the randomised intervention site with their cervical spine motion restriction managed in accordance with the proposed flow chart (appendix B). For these patients unless the exclusion criteria apply, no hard collars will be employed.

After the initial six-month intervention/control phase the receiving sites will reverse the process and undertake another six month phase as the control/intervention phase.

Each participant enrolled will be followed up on site by a research clinician and clinical outcomes measured as stated on the Computerised Tomography (CT) report and/or patient notes. Patient experience outcomes will be collected by a research clinician using a dementia friendly adapted Likert scale type survey prior to discharge or at 72 hours whichever is earliest. Participants will also be

CONFIDENTIAL: Spinal Motion Restriction Feasibility Study (SMRFS).

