10.2. Interim analysis

The Data Monitoring Committee will monitor the accumulating outcome data, and one of their roles is to recommend cessation of recruitment if a clear result has been reached (i.e. if either intervention or control is clearly superior). We suggest that different thresholds of evidence for early termination are adopted if non-collar or collar being more effective, as it is likely that stronger evidence would be needed to change current practice (collar use) if non-collar use is found to be superior. We therefore propose that interim analyses are conducted frequently in the early stages of the trial, so that, if collar use is superior, this can be detected early. Thus we will minimise any risks to patients while producing robust evidence that will change practice.

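### Section 9.3 makes stopping mandatory on any obvious outcome difference, is not confined to safety, and is not reconciled with the stricter tests in 10.2 and 12.7

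*Protocol*

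**What the plan says.** Section 9.3 opens its list with "The study will be stopped prematurely if", so what follows is mandatory. The second bullet is "There is an obvious differentiation between the outcomes of control and intervention groups". The third is separate: "There is a serious adverse event which prevents the ongoing study to be viable".

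Safety halts also appear elsewhere. The opening of section 9 halts the trial for investigation if new neurology develops after transfer. Section 9.2 requires reporting and a halt for an "obvious deterioration/change between pre and post management of the intervention group compared to the control group".

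Two other sections govern stopping on accumulating outcome data:

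- Section 10.2 gives the DMC the role to "recommend cessation of recruitment if a clear result has been reached (i.e. if either intervention or control is clearly superior"). It suggests different evidence thresholds for the two directions, with stronger evidence likely to be needed if non-collar use is superior.
- Section 12.7 has the DMC advise the Steering Committee chair only if two conditions both hold: proof beyond reasonable doubt, and evidence likely to change patient management. The Steering Committee then decides, and it stays blind to interim results unless the DMC asks for the trial to stop.

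The outcomes are listed in the synopsis and sections 4 and 5. They are three times, neurology, fractures or injury, tissue viability, compliance, comfort, pain, understanding, and complications (anxiety, breathing). None is called primary. In the control arm some patients may not tolerate collar, blocks and tape, and "this non-compliance will be recorded for the purposes of the study outcome results" (section 5). Section 3 predicts that "overall patient comfort will be improved" when the collar is omitted.

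**The concern.** A mandatory rule that takes any listed outcome as input can be met by the result the protocol itself anticipates. Patients who find a collar uncomfortable or refuse it would produce a clear difference between groups. That difference says little about whether omitting the collar affects neurology, injury or skin.

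Section 10.1 puts the focus on estimating treatment effects and their uncertainty, and section 10.3 concedes that the study is underpowered. Stopping part-way on tolerability would widen every interval the study exists to produce. The neurological and tissue data would be the thinnest.

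The protocol also gives two answers to one question. Under 9.3 the study stops once a difference is obvious. Under 12.7 the same data would have to meet a demanding two-part test, lead to advice, and then go to another committee for decision.

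**Working it through.** **1. The stopping provisions side by side**

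| | 9.3 bullet | 10.2 | 12.7 |
|---|---|---|---|
| Force | mandatory | recommendation | advice, then decision |
| Standard | an obvious difference | clear superiority | proof beyond reasonable doubt and likely to change management |
| Direction | none stated | stronger evidence if non-collar is superior | either |
| Body | none stated | DMC | DMC advises, Steering Committee decides |

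Section 9.3 cites neither of the others.

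**2. Is the 9.3 bullet limited to safety?** It sits under the safety heading. But serious adverse events have the next bullet, and neurological deterioration has halts in the opening of section 9 and in 9.2. A bullet on outcomes therefore adds something beyond these. Section 10.2 confirms that a superiority stop in either direction is contemplated.

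**3. How easily could compliance alone meet it?** The protocol states no rate, cut-off or timing, so there is no figure of its own to reproduce. The synopsis plans 50 per arm. I take the halfway point, 25 per arm, because at 50 per arm nothing is left to stop. As a stand-in for an obvious difference I use two-sided Fisher exact p<0.01.

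With no non-compliance in the no-collar arm, 6 v 0 gives p = 0.022 and 7 v 0 gives p = 0.0096, so at least 7 of 25 control patients are needed:

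- P(X ≥ 7), X ~ Bin(25, 0.20) = 0.220
- P(X ≥ 7), X ~ Bin(25, 0.30) = 0.659

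One non-compliant patient in the no-collar arm raises the requirement to 10 v 1, and two raise it to 11 v 2. In general, the trigger probability is the sum of Bin(x; 25, p_control) × Bin(y; 25, p_no-collar) over all pairs (x, y) with Fisher p<0.01.

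| Control non-compliance | v 0% | v 5% | v 10% |
|---|---|---|---|
| 20% | 22% | 7% | 2% |
| 30% | 66% | 28% | 12% |

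At p<0.001, 10 v 0 is needed (p = 0.0006), and P(X ≥ 10) at 20% is 1.7%.

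The 5% and 10% columns matter. Section 3 omits only the collar, and the data form in 7.6 has one non-compliance field for every participant, so blocks and tape can be refused in either arm.

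**4. What the neurological data would show by then.** Section 3 cites confirmed spinal cord injury in less than 0.5% of potential cases. Taking 0.5% as an upper figure, the chance of even one case is 1 − 0.995^50 = 22% in 50 patients (25 per arm) and 1 − 0.995^100 = 39% in the full 100.

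**5. Cost in precision.** For a difference between two proportions near 50%, the 95% half-width is 1.96 × √(2 × 0.25/n). That is 0.196 at n = 50 and 0.277 at n = 25, or 1.41 times wider. Clustering by site and period is ignored in steps 3 and 5.

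**The case against.** The strongest reply is that sections 10.2 and 12.7 govern in practice. A DMC bound by proof beyond reasonable doubt would not stop because patients dislike collars, and 10.2 asks for more evidence in exactly that direction. Section 10.2 also says frequent early looks are meant to detect an advantage of the collar and so limit risk. The position of 9.3 under safety, and the similar wording in 9.2, suggest harm was in mind. This stands as evidence of intent. It does not cure the text: 9.3 is mandatory, refers to none of those provisions and lists serious adverse events separately.

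A reader might infer more than the documents support:

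- *Compliance and comfort differ by construction.* This is true only of refusing the collar itself. Other restraint can be refused in both arms, and comfort is an expected effect that the study is meant to estimate.
- *The study could stop with no clinical difference at all.* The protocol classes compliance as a participant clinical outcome, so a stop on compliance is not that. The defensible statement concerns neurological, injury and tissue outcomes.
- *Many outcomes and looks make a false stop near certain.* With 11 independent null outcomes and six looks, simulation gives 84% at nominal p<0.05 but about 4% at p<0.001. The protocol fixes neither looks nor cut-off, and the 12.7 standard is not p<0.05.
- *The 50-per-arm probabilities show early stopping.* That is the full planned sample.

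**Conclusion.** The point holds as a conflict within the protocol and a stated rule that can misfire. Followed literally, 9.3 could end the study on its anticipated tolerability result, under a standard that 10.2 and 12.7 do not share and with no body assigned to apply it. This comes from protocol wording, so a later analysis plan would not remove it.

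The size is uncertain. On the assumptions above, the chance that compliance alone triggers the rule halfway runs from 2% to 66% at p<0.01, and is under 2% at p<0.001 for 20% v 0%. It is material if collar intolerance is common and other non-compliance is rare, and small otherwise. The rates, the cut-off and the halfway look are all assumptions. The textual conflict does not depend on them. It should be corrected, but it does not invalidate the design.

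**What to change.** Reconcile 9.3 with 10.2 and 12.7:

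- Replace the free-standing outcomes bullet in 9.3 with a reference to the DMC test in 12.7 and the Steering Committee decision that follows it.
- State there that an expected difference in compliance, or in the experience outcomes of comfort and understanding, does not meet that test on its own.
- Leave it to the sponsor and the DMC to specify which harms count as safety grounds, including pressure damage and breathing complications in either arm. The halts in section 9 and 9.2 are not altered by this change.

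The cost is a few sentences in the protocol and matching text in any DMC charter. The downside is that the study would not stop early on a tolerability benefit alone.

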10. STATISTICS AND ANALYSIS

The sub-headings given below are suggestions. Add/delete as appropriate.

10.1. Description of Statistical Methods

Describe the statistical methods to be employed, including timing of any planned interim analysis(es).

The primary analysis will be by intention to treat, comparing the outcomes between all participants randomised to Intervention (non-collar) and all those randomised to Control (normal practice). The focus of the analysis will be on estimation of treatment effects and the uncertainty around them. A detailed statistical analysis plan will be developed by the trial statistician.

Results will be presented as estimates of the treatment effect with 95% confidence intervals. Dichotomous outcomes will be analysed using logistic regression models, both unadjusted and adjusted for appropriate covariates. Time to event outcomes such as time on-scene or time to CT will be analysed using time to event techniques. Continuous outcomes will be analysed by regression methods and the results presented as the difference in means between the groups and 95% confidence intervals. Reporting of analyses will follow CONSORT guidelines.

The following exploratory analyses will be used to investigate potential modifiers of the treatment effect of non-collar use:

- Age
- Mechanism
- Compliance

The free text from participant and clinician experience questionnaires will be managed and explored with NVivo qualitative data analysis Software; QSR International Pty Ltd. Version 11, 2015. Coding will be undertaken and reviewed to identify emerging themes (Saldaña, 2013) (including theoretical and conceptual). As data will be collected concurrently, constant comparison will undertaken throughout and new codes identified for qualitative thematic analysis. The data analysis framework approach recommended by Pope et al. (2000) will be used throughout the study.

10.2. Interim analysis

The Data Monitoring Committee will monitor the accumulating outcome data, and one of their roles is to recommend cessation of recruitment if a clear result has been reached (i.e. if either intervention or control is clearly superior). We suggest that different thresholds of evidence for early termination are adopted if non-collar or collar being more effective, as it is likely that stronger evidence would be needed to change current practice (collar use) if non-collar use is found to be superior. We therefore propose that interim analyses are conducted frequently in the early stages of the trial, so that, if collar use is superior, this can be detected early. Thus we will minimise any risks to patients while producing robust evidence that will change practice.

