1. SYNOPSIS

Study Title	Spinal Motion Restriction Feasibility (SMRF) Study. A prospective randomised two centre comparative study to determine if there is a difference in clinical outcomes and patient experience comparing Spinal Motion Restriction techniques which include the traditional use of a rigid cervical spine collar versus the omission of a rigid collar.			
Internal ref. no. / short title	Spinal Motion Restriction Feasibility (SN	IRF) Study.		
Protocol Version	V1.1			
Protocol Date	24/01/2020			
Study Design	A prospective randomised two centre co	omparative intervention study.		
Study Participants	Patients who have experienced a mechanism of injury that would suggest a potential SCI.			
Planned Sample Size	50 intervention participants, 50 control	participants and 100 clinicians		
Planned Study Period	16 months in total (6 months intervention/control followed by 6 months control/intervention at each of two sites. 1 month training for clinicians and research assistants with 3 months data collation, analysis and writing up of conclusions/discussion).			
Number of Study Sites	Three. North East Ambulance service Northumbria Specialist Emergency Care			
	Objectives	Outcome Measures		
Participant Clinical Outcomes	To compare the clinical outcomes of Spinal Motion Restriction principles where intervention group omit the use of rigid collar on potential SCI versus current standard immobilisation practices which includes the use of rigid collar.	 Time: on scene, to scan, in ED. Neurology (Gross) Fractures/Injury Tissue Viability/Pressure sores Compliance 		
Participant Experience	To compare the patient experience outcomes of Spinal Motion Restriction principles where intervention group omit the use of rigid collar on potential SCI versus current standard immobilisation practices which • Comfort • Pain • Understanding • Complications (anxiety, breathing)			

	includes the use of rigid collar.	
Clinician Experience	To compare the clinicians experience of Spinal Motion Restriction principles where intervention group omit the use of rigid collar on potential SCI versus current standard immobilisation practices which includes the use of rigid collar.	Clinician experience (Qualitative)

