3. BACKGROUND AND RATIONALE

Within the United Kingdom (UK), Cervical Spinal Cord Injury (SCI) is a rare event. Traditional three-point immobilisation for spinal stabilisation has been the standard clinical practice for trauma patients with suspected cervical SCI for over 50 years.

The literature highlights a variable global incidence of traumatic SCI of between 9.2 and 246 per million persons per year with a prevalence of 236 to 1,298 per million population (Furlan et al., 2013). In their pre-hospital study Oteir et al. (2016) estimated that of the 106,059 patients who were identified as having potential traumatic SCI, less than 0.5% had confirmed SCI.

Contemporary literature and consensus reports are now challenging traditional practices in favour of a pragmatic second generation of supportive techniques that follow patient centred Spinal Motion Restriction principles. Spinal Motion Restriction principles include moving away from the routine application of rigid collars and back boards, encouraging self-extrication when appropriate, manual in line stabilisation and alternative approaches to Spinal Motion Restriction while improving patient comfort. These principles empower clinicians to tailor their approach to Spinal Motion Restriction and ensure effective and safe patient centred care.

Initial recognition of the need for immobilisation was documented by Rogers (1957) who analysed a case series involving 77 patients who all had significant spinal injuries. Of these 77 cases it was noted that 8 patients developed new or worsening symptoms after arrival at the hospital. Upon reflection, it was hypothesised that if these patients had an adjustable neck brace fitted for the purposes of extrication and transfer then some of these deteriorations may have been avoided.

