10.3. The Number of Participants

This will be a feasibility study and as such an underpowered study with no power calculations. It is expected that if the results are favourable then a full multi-centred clinical trial will follow.

As such, a sample size of 50 participants per site (JCUH and NSECH) as well as 100 (NEAS) clinicians will be expected over the 6 month study period (N=200). It is unknown how many participants will drop out of the study, however, due to a single study visit it is believed that there will be a very low drop/withdraw rate.

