12.7. Data Monitoring Committee

The Data Monitoring Committee will consist of independent experts with relevant clinical research, and statistical experience. During the period of recruitment into the study, interim analyses of the accumulating data will be supplied, in strict confidence, to the Data Monitoring Committee, along with any other analyses that the committee may request. The frequency of these analyses will be determined by the committee.

The Data Monitoring Committee will advise the Chair of the Study Steering Committee if, in their view, the randomised comparisons have provided both (i) 'proof beyond reasonable doubt' that for all, or some, the treatment is clearly indicated or clearly contra-indicated and (ii) evidence that might reasonably be expected to materially influence future patient management. Following a report from the Data Monitoring Committee, the Steering Committee will decide what actions, if any, are required. Unless the Data Monitoring Committee request cessation of the trial the Steering Committee and the collaborators will remain ignorant of the interim results.

The membership of the DMC is:

[name]. Northumbria University.

[name]. North East Ambulance Service Clinical Audit.

[name]. North East Ambulance Service.

[name]. North East Ambulance Service.

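### Section 10.2 says early interim looks will detect collar superiority and minimise risk, but for rare neurological deterioration a between-arm comparison at 50 or fewer per arm cannot do this

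*Protocol*

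**What the plan says.** Protocol section 10.2 gives the Data Monitoring Committee the task of recommending that recruitment stop if either arm is clearly superior. It proposes frequent looks early in the trial, "so that, if collar use is superior, this can be detected early. Thus we will minimise any risks to patients". It names no outcome, test, level or number of looks, and suggests a different evidence threshold for each direction.

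The planned size in the synopsis is "50 intervention participants, 50 control", and section 10.3 states: "This will be a feasibility study and as such an underpowered study with no power calculations".

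Section 3 cites a pre-hospital study of potential traumatic spinal cord injury in which "less than 0.5% had confirmed SCI". Section 6.3 excludes patients with obvious new neurology and those with GCS of 13 or less. The risk statement in section 3 names compromised neurology after poor handling.

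Section 9 holds a separate provision: "If there should be a case of new neurology developing post transfer during the study period the trial would need to be halted", pending investigation. Section 9.2 adds a halt for obvious deterioration. On routing, section 9.2 says "All serious adverse events should be reported to the site primary investigator and chief investigator", with related and unexpected events also going to the ethics committee. Section 12.7 says "interim analyses of the accumulating data will be supplied, in strict confidence, to the Data Monitoring Committee", together with any other analyses the committee requests.

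**The concern.** Section 10.2 presents the between-arm looks as the means by which a disadvantage of omitting the collar would be found early and patients protected. That is a claim about what the design can do, and no stopping boundary chosen later can add information the design does not collect. The serious risk is neurological deterioration, which the protocol's own background suggests is rare in this population. If the looks cannot show an excess of it, a run of looks without a difference may be taken as reassurance by the monitoring, steering and ethics committees. That matters more here because patients are treated first and asked for consent afterwards (section 7.3).

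**Working it through.** The protocol gives no power, detectable difference or stopping boundary, so there is no figure of its own to reproduce beyond the sizes: 50 + 50 patients plus 100 clinicians = 200, which agrees with section 10.3.

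**Inputs**
- 50 per arm at the end (synopsis); 25 per arm as an illustrative early look (assumption).
- Control risk of deterioration 0.5%. This is an assumption, set at the ceiling of the cited rate of confirmed injury (section 3).
- No-collar risk 5%, ten times the control risk (assumption).
- Two-sided 5%, matching the 95% intervals in section 10.1; one-sided 10% as a lenient alternative.
- Individual randomisation and no dropout, both favourable to the plan.

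**Expected events.** 50 × 0.005 = 0.25 per arm. If both arms have 0.5% risk, the chance of no event in 100 patients is 0.995^100 = 61%.

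**Smallest significant split.** Fisher exact p-values for k events v 0:

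| Per arm | Split | Two-sided p | One-sided p |
|---|---|---|---|
| 25 | 4 v 0 | 0.110 | 0.055 |
| 25 | 5 v 0 | 0.0502 | 0.025 |
| 25 | 6 v 0 | 0.022 | 0.011 |
| 50 | 4 v 0 | 0.117 | 0.059 |
| 50 | 5 v 0 | 0.056 | 0.028 |
| 50 | 6 v 0 | 0.027 | 0.013 |

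The two-sided 5% level therefore needs 6 v 0 at either size: 6/25 = 24% or 6/50 = 12% of the no-collar arm. The one-sided 10% level needs 4 v 0. At 10 per arm, 5 v 0 is needed (two-sided). None of this depends on the assumed control risk.

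**Power.** Sum P(X = i) × P(Y = j) over all splits with i > j that reach the level, where X ~ Bin(n, 0.05) and Y ~ Bin(n, 0.005):

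| Per arm | Two-sided 5% | One-sided 10% |
|---|---|---|
| 25 | 0.1% | 3% |
| 50 | 3% | 19% |

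With a control risk of zero, the figures are still 0.1% and 3% at 25, and 4% and 24% at 50. Six unadjusted two-sided looks (10, 20, 25, 30, 40 and 50 per arm; 20,000 simulated trials) give about 3% in all. At 50 per arm, 80% power two-sided needs a no-collar risk of about 17%.

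**What a null result leaves open.** After zero events in n, the two-sided 95% upper limit is 1 − 0.025^(1/n):
- n = 25: 13.7%
- n = 50: 7.1%

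**The section 9 halt.** The chance of at least one no-collar event is 1 − (1 − p)^n. At p = 5% it is 72% in 25 patients and 92% in 50. At p = 0.5% it is 12% and 22%. A halt at the first case would normally come well before 5 or 6 events accumulated.

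**Common outcomes, for contrast.** For 20% v 50% on a yes/no outcome, normal-approximation power is 89% at 50 per arm and 61% at 25.

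**The case against.** Section 10.2 names no outcome. It may be meant for all accumulating data, including pain, breathing problems, pressure sores, times and compliance. That stands: a very large difference in a common outcome could show, so the point is confined to rare neurological harm.

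The protocol admits it is underpowered and puts estimation first, so Fisher significance is a yardstick it never adopts. Also true, but section 10.2 speaks of detecting superiority, and the exact limits give the same message without a test.

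The 0.5% is a cited figure for confirmed injury, not a design assumption. Section 3 also reports deterioration in 8 of 77 and 29 of 958 patients, though in series of spinal injuries rather than suspected ones. The 6 v 0 requirement is unaffected.

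Four stronger readings are tempting and not supported:
- **That the trial has no safeguard.** The section 9 halt is real and does not depend on a comparison.
- **That no threshold could help.** Power moves from 3% to 19% at 50 per arm with the level, and a one-case trigger reacts far more often.
- **That early data would look the same under a tenfold risk.** An event-free look at 25 v 25 has probability 0.995^50 = 78% with equal 0.5% risks, but 0.95^25 × 0.995^25 = 24% if the no-collar risk is 5%.
- **That the committee is denied individual cases.** It monitors outcome data, gross neurology is a listed outcome, and it may request further analyses. What is missing is automatic routing.

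**Conclusion.** The claim in section 10.2 is wrong as written for neurological deterioration. At 50 or fewer per arm, a conventional between-arm comparison has 0.1% to 3% power against a tenfold risk at two-sided 5%, and 3% to 19% at one-sided 10%. Two crossover sites carry less information than individual randomisation, so these figures are optimistic. The power figures rest on the assumed risks; the 6 v 0 requirement and the 7.1% limit do not.

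The case-based halt is what would act, so the looks add almost nothing for this outcome. The defect is a safety property credited to the wrong mechanism. It should be corrected because a null look could be misread and the correction is cheap.

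**What to change.** 1. **Section 10.2.** Withdraw the early-detection and risk-minimising claim for neurological harm. State that between-arm looks at 50 or fewer per arm cannot detect a plausible difference in neurological deterioration, and refer to the case-based halt in section 9.
2. **Sections 9.2 and 12.7.** Copy each report of new or worse neurology, and each death, in either arm, to the Data Monitoring Committee when it goes to the chief investigator. List receipt of these reports among the committee's tasks.
3. **Each look and the final report.** Give neurology as counts and denominators per arm with exact confidence limits, and do not present the absence of a difference as evidence of safety.

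Items 1 and 3 are wording and presentation. Item 2 uses the existing serious adverse event form and adds a little committee work. The protocol gives up a favourable claim. No treatment, clinical or stopping rule is altered.
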